10.6.3.2. Iron Endpoints

Iron Endpoints
Iron Medications

 During the study, subjects may be receiving iron in multiple routes, including: 
 IV iron Oral iron Other iron (including intramuscular, subcutaneous, and hemodialysis/dialysate) Note: The iron route categories above will be determined using the route on the Prior/Concomitant Medication – Iron Therapy record. In addition, ferric citrate records recorded on the Prior/Concomitant Medication – Metabolic Bone Disease Therapy eCRF form will also be summarized as oral iron use.
Baseline Iron Use

 The number and percentage of subjects in the following iron use categories at baseline will be summarized: 
 IV iron use only Oral iron use only Other iron use only IV and oral iron use only IV and other iron use only Oral and other iron use only

CONFIDENTIAL

201410

Iron Endpoints	

 ○ IV, oral, and other iron use ○ No iron use ● When determining baseline iron use, the gap factors mentioned below in the IV iron standardization algorithm will be applied to the end date for each iron record, and the baseline period of 10 weeks before the Randomization date until the day before the Randomization date will also be used. 	
Standardized IV Iron Dose (mg/week) to Determine Iron Management Action	

 ● In order to compare between IV iron records, to determine the action taken with IV iron therapy in the 8 weeks following the date the IV management threshold was met, the dose of IV iron in each associated record will be standardized in terms of mg/month. ● IV iron therapy concomitant medication records that occur or are ongoing during the 8 weeks following the date the IV management threshold was met (inclusive), will be selected and ordered by start and end date. 
 ○ If there is a record has a start date on the date the IV management threshold was met, and a prior record has an end date on the day before the IV management threshold was met, this prior record will be selected and considered as well. ● The standardization will be carried out with the following formula: 
 ○ Standardized IV iron dose (mg/week) = IV iron drug dose (mg) * frequency 	
Note: Frequency defined as follows:	
Frequency (from eCRF)	Frequency (for standardization formula)
2 times per week	2
3 times per week	3
4 times per week	4
5 times per week	5
BID	14
Once daily	7
One time dose	1
Every 12 Hours	14
Every 2 weeks	0.5
Every 4 weeks	0.25
Once a month	0.23
Once a week	1
TID	21
Standardized Baseline IV Iron Dose (mg/month)	

 ● In order to calculate the baseline average monthly IV iron dose, the dose of IV iron will be standardized to obtain a continuous single unit IV iron dose in terms of mg/month for the period from 10 weeks before the Randomization date to the day before the Randomization date. ● IV iron therapy concomitant medication records that occur or are ongoing during the period from the (the Randomization date – 10 weeks) to the Randomization date will be selected and ordered by start and end date. 	

CONFIDENTIAL

201410

Iron Endpoints		

 The standardization will be carried out with the following formula: 
 Standardized IV iron dose (mg/week) = IV iron drug dose (mg) * frequency 		
Note: Frequency and Gap Factors defined as follows:		
Frequency (from eCRF)	Frequency (for standardization formula)	Gap Factor
2 times per week	2	2.5 days
3 times per week	3	1.33 days
4 times per week	4	0.75 day
5 times per week	5	0.4 day
BID	14	0 days
Once daily	7	0 days
One time dose	1	n/a
Every 12 Hours	14	0 days
Every 2 weeks	0.5	13 days
Every 4 weeks	0.25	27 days
Once a month	0.23	29 days
Once a week	1	6 days
TID	21	0 days

 If the frequency of the record is not 'one time dose', then duration is calculated as follows: 
 If the concomitant medication record start date \geq Randomization date, the duration of the record is 0. If the concomitant medication record end date + gap factor < (Randomization date – 10 weeks), the duration of the record is 0. If the concomitant medication record end date + gap factor \geq (Randomization date – 10 weeks) or the record is ongoing, the duration of the record will be calculated as Stop Date – Start Date +1 day where: 
 Start date will be the latest of (concomitant medication record start date and the Randomization date – 10 weeks). Stop date will be the earliest of (concomitant medication record stop date + gap factor and the day before randomization). If the frequency of the record is 'one time dose', then: 
 If concomitant medication record start date < Randomization date – 10 weeks, or if Randomization date \leq concomitant medication record start date, then duration of the record is 0. If Randomization date – 10 weeks \leq concomitant medication record start date < Randomization date, then: 
 Frequency (for standardization formula) = 1 Duration = 7 days The total dose for each IV iron record will be: Standardized dose*duration/7 days A weighted mean will then be used to obtain the baseline monthly IV iron dose: 		

CONFIDENTIAL

201410

Iron Endpoints		

 ○ Mean baseline monthly IV iron dose = $[(\text{IV iron total dose}_{\text{Record 1}}) + \dots + (\text{IV iron total dose}_{\text{Record n}})] / [(\text{Randomization Date} - \text{Screening Week -2 Visit Date}) / 30.4375 \text{ days}]$. 		
Standardized IV Iron Dose (mg/month) from Randomization to Week 52		

 ● In order to calculate the average monthly IV iron dose from Randomization to Week 52, the dose of IV iron will be standardized to obtain a continuous single unit IV iron dose in terms of mg/month for the period from the Randomization date to the Week 52 visit date while the subject is on treatment and before their first RBC or whole blood transfusion. 
 ○ Note: Subjects who are randomized but never treated will not have a value for average monthly IV iron from Randomization to Week 52. ● IV iron therapy concomitant medication records that occur or are ongoing during the period from the subject's Randomization date – 10 weeks to the Week 52 visit date will be selected and ordered by start date and end date. ● The standardization will be carried out with the following formula: 
 ○ Standardized IV iron dose (mg/week) = IV iron drug dose (mg) * frequency 		
Note: Frequency and Gap Factors defined as follows:		
Frequency (from eCRF)	Frequency (for standardization formula)	Gap Factor
2 times per week	2	2.5 days
3 times per week	3	1.33 days
4 times per week	4	0.75 day
5 times per week	5	0.4 day
BID	14	0 days
Once daily	7	0 days
One time dose	1	n/a
Every 12 Hours	14	0 days
Every 2 weeks	0.5	13 days
Every 4 weeks	0.25	27 days
Once a month	0.23	29 days
Once a week	1	6 days
TID	21	0 days

 ● If the frequency of the record is not 'one time dose', then duration is calculated as follows: 
 ○ If the concomitant medication record start date > earliest of (treatment stop date +1 and Week 52 visit date), the duration of the record is 0. ○ If the concomitant medication record end date + gap factor < Randomization date, the duration of the record is 0. ○ If the concomitant medication record end date + gap factor \geq Randomization date or the record is ongoing, the duration of the record will be calculated as Stop Date – Start Date +1 day where: 
 ▪ Start date will be the latest of (concomitant medication record start date, randomization date, treatment start date). 		

CONFIDENTIAL

201410

Iron Endpoints		

 ▪ Stop date will be the earliest of (concomitant medication record stop date + gap factor, first transfusion date (RBC or whole blood), treatment stop date + 1, and the Week 52 visit date). • If the frequency of the record is 'one time dose', then: 
 ○ If concomitant medication record start date < treatment start date, or if earliest of (first transfusion date (RBC or whole blood), treatment stop date + 1 and Week 52 visit date) < concomitant medication record start date, then duration of the record is 0. ○ If latest of (Randomization date, treatment start date) ≤ concomitant medication record start date ≤ earliest of (first transfusion date (RBC or whole blood), treatment stop date + 1 and Week 52 visit date), then: 
 ▪ Frequency (for standardization formula) = 1 ▪ Duration = 7 days • The total dose for each IV iron record will be: Standardized dose*duration/7 days • A weighted mean will then be used to obtain the monthly IV iron dose from Randomization to Week 52: Mean monthly IV iron dose from Randomization to Week 52 while on treatment = $[(IV \text{ iron total dose}_{Record 1}) + \dots + (IV \text{ iron total dose}_{Record n})] / \{[\text{earliest of (treatment stop date + 1, Week 52 Visit Date)} - \text{treatment start date} + 1] / 30.4375 \text{ days}\}$. 		
Standardized Monthly IV Iron Dose (mg/month) from Week 28 to Week 52 (EP Average Monthly IV Iron Dose)		

 • In order to calculate the average monthly IV iron dose from Week 28 to Week 52, the dose of IV iron will be standardized to obtain a continuous single unit IV iron dose in terms of mg/month for the period from the Week 28 visit date to the Week 52 visit date while the subject is on treatment and before their first RBC or whole blood transfusion. 
 ○ Note: Subjects who are randomized but never treated, who have a RBC or whole blood transfusion, or who permanently discontinue randomized treatment on or before the Week 28 visit date will not have a value for average monthly IV iron from Week 28 to Week 52. • IV iron therapy concomitant medication records that occur or are ongoing during the period from the subject's Week 24 visit date to the Week 52 visit date will be selected and ordered by start date and end date. • The standardization will be carried out with the following formula: 
 ○ Standardized IV iron dose (mg/week) = IV iron drug dose (mg) * frequency 
Note: Frequency and Gap Factors defined as follows:
		
Frequency (from eCRF)	Frequency (for standardization formula)	Gap Factor
2 times per week	2	2.5 days
3 times per week	3	1.33 days
4 times per week	4	0.75 day
5 times per week	5	0.4 day
BID	14	0 days
Once daily	7	0 days
One time dose	1	n/a

CONFIDENTIAL

201410

Iron Endpoints		
Every 12 Hours	14	0 days
Every 2 weeks	0.5	13 days
Every 4 weeks	0.25	27 days
Once a month	0.23	29 days
Once a week	1	6 days
TID	21	0 days

- If the frequency of the record is not 'one time dose', then duration is calculated as follows:
 - If the concomitant medication record start date > earliest of (treatment stop date + 1 and Week 52 visit date), the duration of the record is 0.
 - If the concomitant medication record end date + gap factor < Week 28 visit date, the duration of the record is 0.
 - If the concomitant medication record end date + gap factor \geq Week 28 visit date or the record is ongoing, the duration of the record will be calculated as Stop Date – Start Date +1 day where:
 - Start date will be the latest of (concomitant medication record start date, and the Week 28 visit date).
 - Stop date will be the earliest of (concomitant medication record stop date + gap factor, first transfusion date (RBC or whole blood), treatment stop date + 1, and the Week 52 visit date).
- If the frequency of the record is 'one time dose', then:
 - If concomitant medication record start date < Week 28 visit date, or if earliest of (first transfusion date (RBC or whole blood), treatment stop date + 1 and Week 52 visit date) < concomitant medication record start date, then duration of the record is 0.
 - If Week 28 visit date \leq concomitant medication record start date \leq earliest of (first transfusion date (RBC or whole blood), treatment stop date +1 and Week 52 visit date), then:
 - Frequency (for standardization formula) = 1
 - Duration = 7 days
- The total dose for each IV iron record will be: Standardized dose*duration/7 days
- A weighted mean will then be used to obtain the monthly IV iron dose from Week 28 to Week 52:
 Mean monthly IV iron dose from Week 28 to Week 52 while on treatment =

$$\frac{[(IV \text{ iron total dose}_{\text{Record } 1}) + \dots + (IV \text{ iron total dose}_{\text{Record } n})]}{[\{\text{earliest of (treatment stop date + 1, Week 52 Visit Date)} - \text{Week 28 Visit Date} + 1\}/30.4375 \text{ days}]}$$

Iron Use by Quarter

 • The number and percentage of subjects in the following iron use categories defined by route will be summarized by quarters listed below for Average Quarterly IV Iron Dose: 
 ○ IV iron use only ○ Oral iron use only ○ Other iron use only ○ IV and oral iron use only ○ IV and other iron use only ○ Oral and other iron use only

CONFIDENTIAL

201410

Iron Endpoints

 ○ IV, oral, and other iron use ○ No iron use ● When determining iron use by quarter, the gap factors mentioned in the IV iron standardization algorithm will also be applied to the end date for each iron record. ● Although baseline iron use is defined based on a period of 10 weeks, it will also be included in summaries of iron use by quarter.
Average Quarterly IV Iron Dose

 ● The standardized IV iron (mg/month) dose will be summarized by quarters, where quarters will be defined using study visits as follows: 
 ○ Baseline ○ For summaries of on & off treatment IV iron dose: 
 ▪ Quarter 1 = [Randomization date – Week 12) ○ For summaries of on-treatment IV iron dose: 
 ▪ Quarter 1 = [Treatment start date + 1 – Week 12) ▪ Quarter 2 = [Week 12 – Week 24) ▪ Quarter 3 = [Week 24 – Week 36) ▪ Quarter 4 = [Week 36 – Week 48) ● To determine the planned start date and end date of quarters, the visit end date (from the SV domain) will be used. If there is not a corresponding visit, or if the subject is missing that visit, the planned visit date (Randomization date + 7*x) will be used, where x is the scheduled week (e.g., Week 24, x = 24). ● A subject's quarterly average IV iron dose will end at the earliest of the following: 
 ○ For summaries of on & off treatment IV iron dose: death date, study completion/withdrawal date, and the planned quarter end date. ○ For summaries of on-treatment IV iron dose: death date, first transfusion (RBC or whole blood), study completion/withdrawal date, treatment stop date + 1, and the planned quarter end date. ● The standardization algorithm for IV iron described earlier in the table will be used to determine the standardized IV iron dose (mg/month) during each quarter. ● Although the standardized baseline IV iron dose is defined based on a period of 10 weeks, it will also be included in summaries of average quarterly IV iron dose.
TIBC

 ● TIBC will be calculated automatically by the central laboratory using: 
 ○ $TIBC = UIBC + \text{total iron}$
TSAT

 ● TSAT will be calculated automatically by the central laboratory using: 
 ○ $TSAT = 100 * (\text{Serum Iron}/TIBC)$
Average Quarterly TSAT and Ferritin

 ● The average TSAT and Ferritin values will be summarized by quarters, where quarters will be defined as they are for Average Quarterly IV Iron Dose, with the following exception: 
 ○ Baseline average quarterly ferritin and TSAT will take the average of all available records before or on randomization ferritin and TSAT values.

CONFIDENTIAL

201410

Iron Endpoints
Note: any unscheduled values falling within these quarters will be used in the calculation of the quarterly average value.
Meeting Iron Management Criteria
Iron therapy will be administered if at any visit: 
 Ferritin \leq 100 ng/mL and/or TSAT \leq 20% All iron must be stopped if at any visit: 
 Ferritin > 800 ng/mL and TSAT >20%, or TSAT > 40% Subjects meeting iron management criteria requiring starting and stopping of iron administration on the same day: 
 Ferritin \leq100 ng/mL and TSAT > 40%

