4. STUDY DESIGN

4.1. Overall Design

[figure not shown]
- This is a randomized, open-label (sponsor blind), active-controlled, parallel-group, multi-center study in subjects with anemia associated with CKD who are not regularly using routine erythropoiesis-stimulating agent (ESA) users and who are initiating dialysis.
- The study will comprise three study periods: a screening period (2 weeks*), a 52-week active treatment period, and a follow-up period (4-6 weeks) ([Figure 1](#)). Weeks 28-52 are defined as the efficacy evaluation period (EP) for the *primary* efficacy comparison.

* Screening period can be extended by an additional 4 weeks for ultrasound examination, IV iron supplementation and/or vitamin B12 treatment as needed.

- A central randomization approach will be used to protect the trial from potential for selection bias due to the open-label design. All subjects will be treated to achieve and maintain an Hgb within a range of 10-11 g/dL.
- Limited ESA use is allowed around the time of dialysis initiation only (see [Section 5.2](#) for definition of “limited use”).
- The treatment period consists of:

- The stabilization period, defined as the period from Day 1 to Week 28 during which randomized treatment will be dose titrated to achieve the appropriate Hgb target.
 - The evaluation period (EP), defined as the period from the end of the stabilization period (Week 28) to Week 52 (titrations may also occur during this treatment period), to assess safety and efficacy.
- Subjects will be stratified by dialysis type (hemodialysis [HD] or peritoneal dialysis [PD]) and by whether their dialysis start is planned or unplanned (urgent).
 - Following stratification, subjects will be randomized 1:1 to receive daprodustat or rhEPO (darbepoetin alfa); all randomized treatments (Section 6.1) will be supplied by GSK.
 - To ensure consistency of treatment across the study there are protocol-mandated algorithms for dose adjustments of daprodustat and rhEPO (Section 6.2), iron management (Section 6.10) and anemia rescue therapy (Section 6.11)
 - An overview of the study design is provided in Figure 1.

Figure 1 Study Schematic

* Screening period may be extended by an additional 4 weeks for ultrasound examination, IV iron supplementation and/or vitamin B12 treatment as needed.

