8.1.1.2. Planned Principal Secondary Efficacy Statistical Analyses

Principal Secondary Efficacy Statistical Analyses: Average Monthly IV Iron Dose
Endpoint(s)

 • Average monthly IV iron dose (mg)/subject from baseline to Week 52
Model Specification

 • Average monthly IV iron dose (mg)/subject from baseline to Week 52 will be determined by calculating the total IV iron dose per subject from Day 1 to the earliest of ((Week 52 visit date, first blood (RBC or whole blood) transfusion date, and treatment stop date + 1 day) which corresponds to the time while the subject was on randomized treatment and before receiving a blood transfusion. This total IV iron dose will be divided by (the number of days from Day 1 to the earliest of (Week 52 visit date, first blood transfusion date (RBC or whole blood), and treatment stop date +1) /30.4375 days). See Section 10.4 for the definition of on-treatment IV iron. • An ANCOVA model will be used to compare the difference in average monthly IV iron dose per subject between arms, adjusting for: 
 ○ Treatment ○ Baseline monthly IV iron dose (see Section 10.5.2) ○ Dialysis type (as randomized, see Section 0) ○ Dialysis start manner (whether dialysis start is planned or unplanned; as randomized, see Section 0).
Model Results Presentation

 • The number and percentage of subjects with baseline IV iron use, on-treatment EP IV iron use, and on-treatment IV iron use to Week 52 will be summarized by treatment. • Average monthly IV iron dose at baseline, while on treatment during the EP, and while on treatment to Week 52 will be summarized by treatment group using mean, standard deviation, minimum, P25, median, P75, and maximum. • The least square (LS) mean estimates and standard errors by treatment group, LS mean difference, two-sided 95% CI and one-sided superiority p-value for the difference in average monthly IV iron dose/subject to Week 52 between the daprodustat and darbepoetin alfa arms from the ANCOVA model will be presented. The number of subjects contributing to the analysis and the associated mean and standard deviation of the baseline and Week 52 values will also be displayed with the results of the ANCOVA model. • A listing of average monthly IV iron dose will be provided including treatment, site ID, unique subject ID, time period, and average monthly IV iron dose to Week 52.

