10.5.2. Baseline Definition & Derivations

10.5.2.1. Baseline Definitions

For all endpoints (except as noted) the baseline value will be the latest non-missing pre-dose assessment on or before the randomization date. This is generally expected to be the pre-dose value from the Day 1 visit, although such values may be missing.

Parameter	Study Assessments Considered As Baseline		Baseline Used in Data Display
	Screening Week - 2	Day 1 (Pre-Dose)	
Efficacy			
Hgb		X	Randomization Date
Monthly IV iron ¹		X	Randomization Date
Iron parameters		X	Randomization Date
Safety			
Subjects who have in-clinic HD: pre-dialysis BP parameters, HR and weight		X	Randomization Date
Subjects who have in-clinic HD: post-dialysis BP parameters, HR, weight, and dry weight ²	X		Week - 2/Randomization Date

CONFIDENTIAL

201410

Parameter	Study Assessments Considered As Baseline		Baseline Used in Data Display
	Screening Week - 2	Day 1 (Pre-Dose)	
Subjects who do not have in-clinic HD: BP parameters, HR, weight, and dry weight		X	Randomization Date
Lipid parameters, clinical chemistry, hematology, other laboratory and hepatobiliary (liver) tests		X	Randomization Date
PRO			
SF-36 domain and component scores		X	Randomization Date
EQ-5D-5L & VAS		X	Randomization Date
PGI-S		X	Randomization Date
CKD-AQ		X	Randomization Date

NOTES :

- Unless otherwise stated, the mean of replicate assessments at any given time point will be used as the value for that time point.

[1]: Baseline monthly IV iron dose will be defined as total IV iron (mg) over the 10 weeks prior to randomization. See Section 10.6.3.

[2]: Post-dialysis baseline values for subjects with in-clinic dialysis will be defined as the latest non-missing pre-dose assessment before the randomization date. This will most often be the value recorded at the Week -2 visit.

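### Baseline monthly IV iron adds up 10 weeks of dosing but divides by the length of screening, overstating it 5.0-fold at 14 days and 1.67-fold at 42 days for baseline users

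*SAP*

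**What the plan says.** The block on standardized baseline IV iron dose in SAP section 10.6.3.2 sets out to produce a dose in mg/month "for the period from 10 weeks before the Randomization date to the day before the Randomization date". Repeated-dose records are cut off at randomization minus 10 weeks and at the day before randomization. One-time doses count in full if given anywhere in that window. The record totals, in mg, are summed. The last line of the block then divides the sum by the days from the "Screening Week -2 Visit Date" to the randomization date, over 30.4375.

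The length of screening comes from Protocol section 4.1: 2 weeks, with the provision "Screening period can be extended by an additional 4 weeks for ultrasound examination, IV iron supplementation" and for vitamin B12 treatment.

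Two other places describe the period of the baseline dose:

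- Note 1 of SAP section 10.5.2.1: "Baseline monthly IV iron dose will be defined as total IV iron (mg) over the 10 weeks prior to randomization". It refers on to section 10.6.3.
- The quarterly dose block of section 10.6.3.2: "Although the standardized baseline IV iron dose is defined based on a period of 10 weeks, it will also be included in summaries".

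The variable is a covariate in the ANCOVA for the principal secondary endpoint (SAP section 8.1.1.2). It is also reported, separately for each arm: "Average monthly IV iron dose at baseline, while on treatment during the EP, and while on treatment to Week 52 will be summarized". It appears again in the quarterly displays and in the baseline characteristics listed in section 10.10.1, which include a row restricted to subjects using IV iron at baseline.

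**The concern.** A rate needs the same period above and below the line. Here 70 days of iron are divided by a period that is nominally 14 days and at most 42 under the protocol. Nothing elsewhere in the SAP corrects the divisor.

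Two things are at stake. First, reported baseline mg/month is too high for every baseline user, and it is displayed next to evaluation-period, to-Week-52 and quarterly mg/month. A reader could see a fall in IV iron use in both arms that did not happen, in a trial whose principal secondary claim is about IV iron.

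Second, the error is not a constant that the regression slope would absorb. It depends on each subject's screening length, and screening can be extended for IV iron itself. Subjects with the same 10-week total can therefore carry covariate values 3-fold apart (5.0/1.67) within the 14 to 42 day range. The order can even reverse: 1000 mg with 42 days of screening scores 725 mg/month, while 500 mg with 14 days scores 1087.

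**Working it through.** The documents give no numerical value for baseline IV iron, so there is no figure to reproduce. The check applies the stated algorithm to simple dosing histories.

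**Inputs**
- Numerator window: randomization minus 70 days to randomization minus 1 day, 70 days inclusive (SAP 10.6.3.2).
- Dose per record: mg/week × days/7; a one-time dose contributes its full amount (SAP 10.6.3.2).
- Month: 30.4375 days (SAP 10.6.1).
- Screening length *d*: 14 days nominal, up to 14 + 28 = 42 days (Protocol 4.1).

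**Formulas**, with *T* the 10-week total in mg
- SAP as written: T / (d/30.4375)
- Matched to the window: T / (70/30.4375) = T / 2.2998
- Ratio: 70/d, independent of T

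**Results**

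| Screening days | Ratio 70/d | T = 1000 mg (100 mg weekly), matched rate 434.8 | T = 500 mg (single dose), matched rate 217.4 |
|---|---|---|---|
| 14 | 5.00 | 2174.1 | 1087.1 |
| 21 | 3.33 | 1449.4 | 724.7 |
| 28 | 2.50 | 1087.1 | 543.5 |
| 42 | 1.67 | 724.7 | 362.4 |

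The single-dose result is the same whether the dose falls 60 or 7 days before randomization. With no IV iron in the window, both versions give 0.

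**What a reader would see.** Take an untransfused subject who stays on 100 mg weekly. The on-treatment rate is 100/7 × 30.4375 = 434.8 mg/month. Against a baseline of 2174.1 (14-day screening) the apparent fall is 1 − 434.8/2174.1 = 80%; against 724.7 (42 days) it is 40%. Use has not changed.

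**Group mean among users.** Let a share *q* have 42-day screening and the rest 14. If dose is unrelated to screening length, the factor is 5(1 − q) + 1.667q. Column three instead assumes that users have lognormal 10-week totals (median 600 mg, log-SD 0.6, mean 600 × exp(0.18) = 718 mg) and that extension adds 500 mg; the factor is then [5(1 − q)·718 + 1.667q·1218] / [(1 − q)·718 + q·1218].

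| q | Dose unrelated | Extension adds 500 mg |
|---|---|---|
| 0.10 | 4.67 | 4.47 |
| 0.50 | 3.33 | 2.90 |
| 0.75 | 2.50 | 2.21 |
| 0.90 | 2.00 | 1.87 |

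**Precision of the ANCOVA.** None of these inputs is in the documents: 25–75% of subjects use IV iron, 10–90% have 42-day screening, and doses follow the two models above. The correlation *c* between the SAP covariate and the matched one then runs from 0.71 to 0.97. If the matched covariate correlates *ρ* with the outcome and the distorted one ρc, residual variance rises by (1 − (ρc)²)/(1 − ρ²) − 1. From unrounded c this is 0.2% to 2.0% at ρ = 0.2, and 1.0% to 9.3% at ρ = 0.4.

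**Type I error.** In simulated null trials (150 per arm, 4000 trials in each of three scenarios), the SAP covariate gave one-sided 2.5% rejection rates of 0.0225 to 0.0235. The Monte Carlo standard error is √(0.025 × 0.975/4000) = 0.0025, so these are consistent with 0.025. The mean treatment estimate was within 0.0015 SD of zero.

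**The case against.** The mismatch itself is hard to dispute; the arguments against concern the reference value and the consequence.

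**Which definition is wrong?** Section 8.1.1.2 sends the covariate to section 10.5.2, where note 1 gives the undivided 10-week total. Measured against that, the 10.6.3.2 formula is not always too high: the ratio is 30.4375/14 = 2.17 at 14 days and 30.4375/42 = 0.72 at 42. This stands to the extent that the SAP holds two definitions of one variable. But note 1 refers on to 10.6.3 and the variable is labelled monthly throughout, so a total divided by 10 weeks' worth of months is the better reading. One could instead shorten the numerator to the screening interval, but the SAP describes the dose as a 10-week quantity in three places. (Its other 10-week references concern categories of iron use by route and add only indirect support.)

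**Does it matter?** The test compares post-randomization dose, both arms share the distortion, and the primary endpoint is untouched. That is right. The precision loss is negligible at a correlation of 0.2, and the larger figures rest on assumptions. The false impression of a fall is a risk, not a certainty.

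**Is the range a bound?** No. Fourteen days is nominal; an actual 7-day interval would give 70/7 = 10-fold.

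**Conclusion.** The concern holds. As written, the formula gives a wrong baseline mg/month for every subject with IV iron in the 10 weeks before randomization, too high by 70/screening days: 5.0-fold at the nominal 14 days and 1.67-fold at 42. These factors need only the SAP's own window and the protocol's screening lengths. The group-mean factors and the precision figures also depend on assumed dosing and screening patterns, and are illustrative.

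The main consequence is a misleading baseline in tables that sit beside on-treatment doses. A second is somewhat weaker covariate adjustment in the only secondary test under multiplicity control. Neither bias in the treatment comparison nor inflation of type I error is expected. This should be corrected, but it does not threaten the trial's conclusions. The to-Week-52 formula in the same section has a separate divisor question for transfused subjects, which is not taken up here.

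**What to change.** In SAP section 10.6.3.2, replace the divisor of the baseline dose by 70/30.4375 (2.30 months) for every subject. In note 1 of section 10.5.2.1, define baseline monthly IV iron as the total IV iron in mg over the 10 weeks before randomization divided by 70/30.4375, so that the two sections agree.

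With this change 100 mg weekly gives 434.8 mg/month and a single 500 mg dose gives 217.4, whatever the length of screening.

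The cost is one formula and one footnote. Data collection and study conduct do not change, because the numerator already requires the 10-week records.
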